#### **IV#2 VISIT**

This visit for the second IV infusion (IV#2) will be conducted at the next scheduled dosing interval (ie, 3 or 4 weeks from IV#1). The following procedures and tests will be performed at the IV#2 visit:

- Vital signs (pre-infusion: SBP and DBP, HR, T, RR)
- Predose blood draw for trough total IgG, IgG subclass, and antibody titer levels for *S. pneumoniae*, *H.influenzae*, and *C. tetani* (tetanus) prior to SC infusion (within 0.5 hour prior to the start of infusion).

Note: This trough IgG sample is the same one that is used for PK blood draw at the 21 or 28 day post-infusion time points.

- Pre-dose measles antibody titer
- IV IGIV-C 10% infusion
- Concomitant medications
- Adverse events including SBIs (subjects with an SBI will discontinue from the study)

Note: Record any SBIs (defined in [Appendix 2](#)), hospitalizations due to infections, and non-serious infections (by category) as detailed in [Section 3.6.3.1](#).

- Record days lost from work/school/daily activities due to infections and treatment

Subjects will return to the clinic 7 days after the IV#2 visit to start the SC Phase of the study which includes weekly infusions of IGSC 20% that will continue for a total 24 weeks.

### 3.6.2.4 SC Phase – SC Administration of IGSC 20%

#### **CONSIDERATIONS FOR SC ADMINISTRATION**

The first 3 weekly doses of SC study drug will be administered in the clinic by medical site personnel. During these clinic visits, subjects will be instructed and informed regarding all aspects of the techniques and procedures needed for self-administration of study drug (which is to begin at SC Week #4). The SC dose calculations will be performed by study clinic personnel and will be verified (double-checked) by another study staff member. The exact SC dose volume to be administered and rate of infusion will be provided to each subject by the clinic personnel. The number and location of SC infusion sites will be determined by the subjects in consultation with the investigator.

SC infusion diary: An IGSC 20% infusion diary will be provided to each subject prior to the first IGSC 20% infusion which may be used to record items including but not limited to: infusion site reactions, concomitant medications (including antibiotics [prophylactic and therapeutic]), and details of study drug administration (location and number of sites, date/clock time of start and end of infusion, dose/volume of each SC dose, duration and rates of infusion). The SC infusion diary may also be used to record days of missed work/school/daily activities due to infections and related treatment.

Note: All infusion site reactions will be recorded. For the subset of local infusion site reactions where the symptoms/signs lead to infusion interruption or discontinuation, require concomitant medication, or have an impact on the general condition of the subject as judged by the Investigator, these will be considered as AEs.

#### **SC WEEK #1 CLINIC VISIT**

Subjects with an SBI identified prior to SC#1 administration will discontinue study. The following procedures and tests will be completed at the SC Week #1 visit:

- A full physical exam prior to IGSC 20% infusion (excluding breast and genitourinary exam)
- Predose Wells Score will be performed as a benchmark prior to first IGSC 20% dose for all subjects ([Appendix 4](#) provides Wells Score and management details; see also [Section 3.6.3.3](#))
- Vital signs (pre-infusion: SBP, DBP, HR, T, RR)
- Body weight (will be used for SC dose calculation)
- Predose laboratory assessments (as outlined in Screening Visit [[Section 3.6.2.1](#)] including hematology, clinical chemistry, special tests, and urinalysis)
- Predose D-dimer sample as a benchmark prior to first IGSC 20% infusion for all subjects
- Predose virus safety retain samples

Collection of virus safety retain samples prior to IGSC 20% infusion as detailed in [Table 3-2](#). Collect samples but test only if the subject exhibits clinical signs and symptoms consistent with hepatitis A virus (HAV), HBV, HCV, HIV, or parvovirus B19 (B19V) infection while participating in the study.

Note: For children at the discretion of the Investigator, virus safety retain samples may be drawn 1 or 2 days prior to SC Week#1 instead of combining with other blood draws on a single day. Collected samples will be tested only if the subject exhibits clinical signs and symptoms consistent with HAV, HBV, HCV, HIV, or B19V infection while participating in the study.

- SC infusion of IGSC 20%
- Concomitant medications
- Adverse events including SBIs

Note: Record any SBIs (defined in [Appendix 2](#)), hospitalizations due to infections, and non-serious infections (by category) as detailed in [Section 3.6.3.1](#).

- Record days lost from work/school/daily activities due to infections and treatment  
IGSC 20% dosage (mg/kg) will be based on the subject's prior IgG replacement regimen and current body weight as described in [Section 3.3](#).
- Site personnel will train subjects/caregivers how to administer IGSC 20% using an infusion SC pump
- Train and distribute SC Infusion Diary with subjects/caregivers (See [Section 3.6.2.4](#))

#### **POST SC#1 DAY 2-4 BLOOD SAMPLING VISIT ONLY**

Obtain a sample for DAT, serum free hemoglobin, and haptoglobin 2-4 days post SC#1.

No other assessments are needed for this blood draw visit.

#### **SC WEEKS #2, #3 CLINIC VISITS**

The objective of these 2 visits is for safety monitoring, for the subject/caregiver to self-administer SC infusions at the clinic, and for additional self-SC administration training and support by the clinical site staff to assure capability for full independent home administration.

- Abbreviated physical exam defined as targeted to symptoms and to include examination of heart, lungs, ears/nose/throat, and with inspection of previous injection sites, and Specific Signs/Symptoms Check for DVT or pulmonary embolus (PE).  
If the following specific signs/symptoms are present, perform Wells Score and blood draw for D-dimer testing ([Appendix 4](#); see also [Section 3.6.3.3](#)):
  - a. Clinical suspicion of possible DVT with unilateral symptomatic leg swelling, accompanied by any of the following pain, warmth, and/or redness
  - b. Medical suspicion of possible PE in a subject presenting with new or worsening dyspnea, tachypnea, chest pain, syncope, and cough in the appropriate clinical setting (cough should not be due to infection, lung disease [eg, asthma, emphysema], or angiotensin-converting enzyme inhibitors)
  - c. Any single alarm symptom such as hemoptysis or cyanosis ([36,37,38](#))
- Vital signs (pre-infusion: SBP, DBP, HR, T, RR)

- Predose Special tests (DAT, serum free hemoglobin, haptoglobin) will be performed at both SC Week #2 and SC Week #3 visits. (These visits represent a 7-day time point after the prior IGSC 20% infusion). Note that additional special tests (DAT, serum free hemoglobin, haptoglobin) will be performed 2-4 days *post SC #2 only* (also noted below as a separate Blood Sampling Visit).
- Observe subject/caregiver self-administration of SC infusion of IGSC 20% in the clinic  
Note: Site personnel will observe (and re-train if needed) subjects/caregivers on administration IGSC 20% using the infusion SC pump
- Concomitant medications
- Adverse events including SBIs  
Note: Record any SBIs (defined in [Appendix 2](#)), hospitalizations due to infections, and non-serious infections (by category) as detailed in [Section 3.6.3.1](#).
- Record days lost from work/school/daily activities due to infections and treatment
- Review SC infusion diary and infusion details with subjects/caregivers

#### **POST SC#2 DAY 2-4 BLOOD SAMPLING VISIT ONLY**

Obtain a sample for DAT, serum free hemoglobin, and haptoglobin 2-4 days post SC#2.

No other assessments are needed for this blood draw visit.

#### **SC WEEKS #5, #9, #17, AND #21 CLINIC VISITS**

The following procedures and tests will be completed at the SC Weeks #5, #9, #17, and #21 visits:

- Abbreviated physical exam with inspection of SC injection sites, and Specific Signs/Symptoms Check.  
If the following Specific signs/symptoms are present, perform Wells Score and blood draw for D-dimer testing ([Appendix 4](#); see also [Section 3.6.3.3](#)):
  - a. Clinical suspicion of possible DVT with unilateral symptomatic leg swelling, accompanied by any of the following pain, warmth, and/or redness
  - b. Medical suspicion of possible PE in a subject presenting with new or worsening dyspnea, tachypnea, chest pain, syncope, and cough in the appropriate clinical setting (cough should not be due to infection, lung disease [eg, asthma, emphysema], or angiotensin-converting enzyme inhibitors)
  - c. Any single alarm symptom such as hemoptysis or cyanosis ([36,37,38](#))
- Vital signs (pre-infusion: SBP and DBP, HR, T, RR)
- Body weight (will be used for SC dose calculation)
- Height SC Week #9, SC Week #17, and SC Week #21 only
- **SC Week #9, SC Week#17only:** Predose laboratory assessments drawn prior to SC infusion (as outlined in Screening Visit [\[Section 3.6.2.1\]](#) including hematology, clinical chemistry, special tests, and urinalysis)

- Predose blood draw for trough total IgG (all visits)
  - **SC Week #9, SC Week#17 only:** IgG subclass, and antibody titer levels prior to SC infusion (within 0.5 hour prior to the start of infusion).
  - Review SC infusion diary and infusion details with subjects/caregivers
  - Observe subject/caregiver self-administration of SC infusion of IGSC 20% in the clinic
  - Concomitant medications
  - Adverse events including SBIs
- Note: Record any SBIs (defined in [Appendix 2](#)), hospitalizations due to infections, and non-serious infections (by category) as detailed in [Section 3.6.3.1](#).
- Record days lost from work/school/daily activities due to infections and treatment

**AWAY FROM CLINIC (SC WEEKS #4, #6, #7, #8, #10, #11, #12, #15, #16, #18, #19, #20, #22, #23, #24)**

Subjects will begin home self-administration of SC infusions of IGSC 20% beginning with the 4th SC infusion. If it is felt by the subject or Investigator that the subject requires additional educational training for administering the study drug SC, additional clinic visits will be scheduled to further train the subject. Subjects will be directed to adhere closely to their individualized dosing regimen and cautioned not to round-up to the whole vial or under dose.

SC infusion diary: The IGSC 20% infusion diary may be used to record items including but not limited to: infusion site reactions, concomitant medications (including antibiotics [prophylactic and therapeutic]), and details of study drug administration (location and number of sites, date/clock time of start and end of infusion, dose/volume of each SC dose, duration and rates of infusion). The SC infusion diary may also be used to record days of missed work/school/daily activities due to infections and related treatment.

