### 3.3.2.3 Subcutaneous Administration Procedures for IGSC 20%

The number of injection sites, infusion rate, and the specific times of the day for the SC infusion may be individualized by the subject and Investigator. The first 3 SC infusions will be given under supervision in the clinic before self-administration at home will be allowed. The selected pump specifically designed for SC infusions will be provided for individual use to each subject prior to the SC Phase and each subject will be trained thoroughly on its use. The PK focus of the study will be emphasized to all the subjects/caregivers. Subjects will be instructed to closely adhere to their individualized dosing regimen accurately and cautioned not to round-up to the whole vial or to under dose. The exact IGSC 20% dose (and dose volume) based on the predetermined adjustment factor and the stable IV dose of IGIV-C 10% will be administered and recorded.

Details regarding infusion rate and infusion administration are located in the pharmacy/study manual. Subjects may use the same anatomical area or rotate anatomical areas for SC infusions throughout the study. No more than 8 infusion sites per infusion will be used. The minimum distance between infusion sites is recommended to be no less than 2 inches. The

target infusion rate will be no greater than 25 mL/hour/site as tolerated by the subject and per the Investigator's discretion; the Investigator will tailor the infusion configuration for each subject. Once the target infusion rate is achieved, it should not be changed in the middle of an infusion unless the subject experiences tolerability issues at that infusion rate. In the event that the subject is not able to tolerate the set infusion rate, the rate may be decreased for better tolerability. Conversely, if the target infusion rate is well tolerated during 2 infusions, an increase of 20% in infusion rate and volume per site is allowed at the discretion of the Investigator at the time of the clinic visit.

The volume infused, number of infusion sites, infusion start date/time, infusion end date/time, the location(s) of infusions, and the initial and final rate of infusion for each infusion site, and other SC infusion information will be recorded in the SC Infusion Diary by the subject/parents or legal guardians. In addition, SC infusion site reactions may be recorded in the diary. Full details regarding the SC Infusion Diary are in [Section 3.6.2.4](#).

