### 3.5.4 Safety Variables

The following safety variables will be assessed in this study:

- Adverse events (AEs), suspected adverse drug reactions (suspected ADRs), adverse reactions (ARs), serious AEs (SAEs), and discontinuations due to AEs and SAEs  
Note: All infusion site reactions will be recorded in the eCRF. For local infusion site reactions where the symptoms/signs lead to infusion interruption or discontinuation, require concomitant medication, or have an impact on the general condition of the subject as judged by the Investigator, they will be considered as AEs.
- Vital signs during clinic visits (systolic blood pressure [SBP] and diastolic blood pressure [DBP], heart rate [HR], temperature [T], respiratory rate [RR])
- Physical Assessments: physical exams will be recorded as normal or abnormal, according to the physician's judgment criteria, and findings will be recorded.
- Laboratory assessments including chemistry, hematology, and urinalysis.
- Total number of non-serious infections and proportion of subjects who experience non-serious infections of any kind (including acute sinusitis, exacerbation of chronic sinusitis, acute otitis media, pneumonia, acute bronchitis, infectious diarrhea, etc.) as determined by the Investigator.

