## 4.3 Adverse Event Definitions

### 4.3.1 Adverse Events

An AE is defined as any untoward medical occurrence in a subject or clinical investigation subject administered a medicinal product or study treatment and that does not necessarily have a causal relationship with this treatment. An AE can therefore be any unfavorable and unintended sign (including any abnormal laboratory finding), symptom, or disease temporally associated with the use of a medicinal product, whether or not considered related to the medicinal product.

Any AE that occurs at any time between the signature of the ICF and last day of the subject's participation in the clinical trial must be reported and recorded in the AE eCRF.

All infusion site reactions will be recorded. For the subset of local infusion site reactions where the symptoms/signs lead to infusion interruption or discontinuation, require concomitant medication, or have an impact on the general condition of the subject as judged by the Investigator, these will be considered as AEs.

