### 5.1.6 Safety Analysis

The safety analyses are based on the safety population.

All AEs, suspected ADRs, ARs, SAEs, and discontinuations due to AEs and SAEs will be summarized by presenting the number of AEs and the number and percentage of subjects with AEs. The summaries will be presented by MedDRA system organ class and preferred term. AE summaries by severity will also be provided. Local infusion site reactions will be similarly summarized. Non-serious infections of any kind (including acute sinusitis, exacerbation of chronic sinusitis, acute otitis media, pneumonia, acute bronchitis, infectious diarrhea, etc.) as determined by the Investigator will also be considered a safety endpoint and will be similarly summarized.

Subjects with deaths, SAEs, and AEs leading to premature discontinuation from the study will be listed and presented in a narrative form.

Adverse events temporally associated with IV or SC administration of study drug will be defined as those occurring during or within 72 hours of completion of an infusion.

Additionally, local infusion site reactions will be tabulated and summarized for the total duration of the study and by IGSC 20% infusion week.

For all laboratory tests and vital signs, the original value and the change from Baseline will be summarized for numeric results and frequency/percentage will be summarized for qualitative results. For laboratory tests with normal ranges, out of normal range values will be flagged and shift tables will be provided.

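### The diary entry for infusion site reactions is optional although all reactions must be recorded and tabulated by infusion week, so mild reactions away from the clinic may be missed or misdated

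*Protocol*

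**What the plan says.** **The duty to record.** Section 3.5.4 states: "Note: All infusion site reactions will be recorded in the eCRF". The Safety Variables part of the synopsis says the same. Section 4.3.1 repeats the duty without naming a source: "All infusion site reactions will be recorded". Under 4.3.1, a local reaction counts as an AE only if it interrupts or stops the infusion, needs concomitant medication, or affects the subject's general condition.

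**The analysis.** Under section 5.1.6, "local infusion site reactions will be tabulated and summarized for the total duration of the study and by IGSC 20% infusion week". The synopsis plans the same table.

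**The diary.** For infusions away from the clinic, section 3.6.2.4 says: "The IGSC 20% infusion diary may be used to record items including but not limited to", followed by a list that starts with infusion site reactions. The general SC considerations in 3.6.2.4 and the Key Assessments part of the synopsis are equally permissive. Section 3.3.2.3 treats the two kinds of entry differently. Volume, number and location of sites, times and rates "and other SC infusion information will be recorded in the SC Infusion Diary by the subject/parents or legal guardians". The text then continues: "In addition, SC infusion site reactions may be recorded in the diary".

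**The concern.** A mandatory duty is fed by an optional source. A blank reaction entry in the diary cannot be told apart from an infusion with no reaction. A reaction below the AE threshold that begins at home and has gone by the next visit may therefore never reach the eCRF, or may be attached to the wrong infusion.

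The by-week table is the output most exposed, because it needs each reaction tied to one infusion. Tolerability is part of the safety objective (section 2.4). A gap of this kind cannot be repaired after database lock.

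**Working it through.** **1. Home and clinic infusions.** Section 3.6.2.4 lists home Weeks 4, 6, 7, 8, 10, 11, 12, 15, 16, 18, 19, 20, 22, 23 and 24, which is 15. The clinic infusions are at Weeks 1, 2, 3, 5, 9, 13, 14, 17 and 21, which is 9. Together they cover Weeks 1 to 24 once each. The home share is 15/24 = 62.5%. For 42 completers this is 42 × 15 = 630 of 42 × 24 = 1008 infusions.

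**2. Wait until the next scheduled clinic visit** (the Final Visit counts as Week 25; the visits for blood sampling only are left out).

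| Wait | Home infusions | Clinic infusions |
|---|---|---|
| 1 week | 4, 8, 12, 16, 20, 24 (6) | 1, 2, 13 (3) |
| 2 weeks | 7, 11, 15, 19, 23 (5) | 3 (1) |
| 3 weeks | 6, 10, 18, 22 (4) | 14 (1) |
| 4 weeks | none | 5, 9, 17, 21 (4) |

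Without a diary entry, capture of a resolved reaction rests on recall over 2 to 3 weeks for 5 + 4 = 9 of the 15 home infusions. The longest waits follow clinic infusions, where a reaction can begin after the subject has left.

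**3. Other routes of capture.**
- *Inspection of injection sites* (SC Weeks 2, 3, 5, 9, 13, 14, 17 and 21) sees what is still visible. It cannot show a resolved reaction or reliably say which of several infusions caused a finding. The Final Visit (3.6.2.6), which follows the infusions of Weeks 22 to 24, lists a full physical exam but no specific site inspection.
- *Diary review* at visits starts from what was entered.
- *The non-leading question* at each visit (4.3.7) is there to elicit AEs, and the reactions at issue fall below the AE threshold.
- *Exclusion criterion 19* requires willingness to complete the diary. It makes no single field mandatory.

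Each route helps. None is a mandatory record made at the time of the event.

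**4. Size, by assumption only.** The protocol gives no reaction rate and no diary completion rate. Let *m* be the share of home reactions that goes unrecorded and *c* the share for clinic infusions. With equal reaction rates per infusion:

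overall loss = (15/24) × *m* + (9/24) × *c*

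With *c* = 0:

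| *m* | Overall loss |
|---|---|
| 0% | 0% |
| 10% | 0.625 × 10% = 6.3% |
| 25% | 0.625 × 25% = 15.6% |
| 50% | 0.625 × 50% = 31.3% |

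If *c* = *m*, the overall loss is *m* itself, and home and clinic weeks are understated alike.

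**The case against.** The strongest reply is that the protocol does not contradict itself on whether reactions are recorded. The duty is unconditional, and the permissive wording attaches to the diary as one instrument. The synopsis and the general part of 3.6.2.4 set the two statements close together, so they can be read as compatible. The sentence for home infusions also covers dose, times and sites, which 3.3.2.3 makes mandatory and 3.3.4 uses for compliance. On its own, then, that sentence does not single reactions out as optional. This stands, and it is why the contrast within 3.3.2.3 carries the point. Compatible wording still leaves the mandatory record without a mandatory source.

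The diary form is not shown and may already contain a reaction field. That also stands, but a field on a form does not make the entry required.

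A reader might infer two stronger things. The first is that local reactions *will* be under-counted. The protocol does not support this, because inspection, diary review, questioning at visits and spontaneous reports all give partial capture. The second is that home weeks will look better tolerated than clinic weeks through recording alone. This is not established either. Reactions to the clinic infusions at Weeks 5, 9, 17 and 21 can start after the visit and then wait longer than any home reaction, so the direction of any distortion is open.

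**Conclusion.** The point holds as a risk and as a matter of wording. Reactions that are not AEs, arise away from the clinic and resolve before the next visit have no mandatory source at the time of the event. They may be under-counted or placed in the wrong week.

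The counts of infusions and waiting times are firm, since they come from the visit schedule. The 0 to 31% overall loss is an illustration. It rests on an assumed 0 to 50% loss at home, equal reaction rates at home and in clinic, and full capture of clinic infusions, and the last of these is doubtful. The primary PK analysis, sample size and error rate are not affected. This is a minor but worthwhile improvement.

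**What to change.** In the synopsis, section 3.3.2.3 and both diary paragraphs of section 3.6.2.4, change *may* to *will* for infusion site reactions. Require a diary entry for every SC infusion, in clinic and at home, stating either that a reaction occurred or that there was none. This aligns those sections with 3.5.4 and 4.3.1 and lets the by-week table separate no reaction from not recorded.

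The cost is a wording change, one diary field if it is not already there, and slight extra effort for subjects, who already enter infusion details in the diary. No dose, visit or analysis changes.
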